5.0 Ethical and Regulatory Obligations

5.1 Study Conduct

- The sponsor/investigator agrees that the study will be conducted according to the protocol, the principles of Good Clinical Practices (GCPs) outlined in 21 CFR parts 50, 56, and 812, the World Medical Association Declaration of Helsinki and the International

Non-Significant Risk Study of a Cochlear Implant Headpiece

Council on Harmonization (ICH) Guidelines, and internal Standard Operating Procedures (SOPs). The sponsor/investigator will conduct all aspects of this study in accordance with all national and local laws of the pertinent regulatory authorities.

- The sponsor/investigator will assure proper implementation and conduct of the study including those duties delegated to other appropriately qualified individuals and Study Staff. The sponsor/investigator and Study Staff will demonstrate due diligence in recruiting and retaining study participants.

5.2 Institutional Review Board and Ethics Committee

- Before initiation of the study, the sponsor/investigator must obtain approval of the research protocol, informed consent form, and any advertisement for subject recruitment, from the governing IRB/IEC complying with the provisions specified in 21 CFR Part 56 and any other applicable regulations. The approval letter must be signed by the IRB chairman or designee, identify the IRB name and address, the clinical protocol by title and/or protocol number, and include the date that approval was granted. The sponsor/investigator is responsible for obtaining continued review of the clinical research at intervals not exceeding one year or as otherwise specified by the IRB.

5.3 Informed Consent

- All informed consent forms and patient information sheets must contain the minimum elements as mandated by FDA (21 CFR Part 50) and ICH guidelines and will be subject to IRB approval.
- Before recruitment and enrollment, each prospective study candidate will be given a full explanation of the study, allowed to read the approved informed consent form, and be provided the opportunity to ask any questions that may arise. Once all questions have been answered and the sponsor/investigator is assured that the individual understands the implications of participating in the study, the subject will be asked to give consent to participate in the study by signing the informed consent form. The sponsor/investigator will provide a copy of the signed informed consent form to each subject.
- If an amendment to the protocol changes the subject participation schedule in scope or activity, or increases the potential risk to the subject, the informed consent form must be revised, submitted to the IRB for review and approval. The revised informed consent form must be used to re-consent a subject currently enrolled in the study if he or she is affected by the amendment. The revised informed consent form must be used to obtain consent from any new subjects who are enrolled into the study after the date of the approval of the amendment.

5.4 Amendments and Deviations

- **Protocol Amendments:** This protocol is to be followed exactly. Changes to the research covered by this protocol must be implemented by formal protocol amendment. A

formal amendment cannot be initiated until regulatory approval is obtained (if applicable) and it has been reviewed and approved by the IRB.

- **Emergency Deviations:** Emergency deviations or modifications may be initiated without IRB approval only in cases where change is necessary to eliminate an immediate apparent hazard to subjects. Emergency deviations or modifications must be reported to the IRB no later than 24 hours after the emergency.
- **Protocol Deviations:** Deviation from the clinical protocol and protocol requirements including ICH/GCP guidelines will be reviewed and evaluated on an ongoing basis, reported to the IRB as necessary and appropriate corrective actions implemented as necessary.

5.5 Health Insurance Portability and Accountability Act (HIPAA)

- All subjects must sign a HIPAA authorization form prior to participation in the study.

5.6 Monitoring of the Study

- A data monitoring committee is not needed for this study as there is no significant risk to participants and the investigation is carried out with a single Principal Investigator.

6.0 Documents and Records

6.1 Pre-Study Documentation Requirements

- Prior to consenting any subjects, the following documents must be available:
 - A copy of this protocol that has been signed and dated by the Principal Investigator and Sub-Investigators
 - A copy of the written IRB approval of the protocol
 - A copy of the written IRB approval of the Informed Consent Form and the approved Informed Consent Form
 - A copy of the curriculum vitae of the Principal Investigator and Sub-Investigators

6.2 Study Documentation

- Study records are comprised of source documents and all other administrative documents.
- Source documentation is defined as any hand-written or computer generated document that contains medical information or test results that have been collected for or is in support of the protocol specifications, e.g., lab reports, clinic notes, subject completed questionnaires, telephone logs, informed consent, etc. All draft, preliminary and pre-

final iterations of a final report are also considered to be source documents, e.g., faxed lab reports and hard copy lab reports, faxed initial results and hard copy final report.

6.3 Device Accountability

- Study equipment will be provided and tracked by Investigators and/or Study Staff.

7.0 Adverse Event Reporting

- All adverse events will be monitored throughout the duration of the study.

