Primary Study Endpoint	Completion of all provided questionnaires that capture subjectively reported headpiece retention and comfort, as compared to baseline.
Primary Safety Endpoint	Cumulative frequency of adverse events and events per participant
Safety Parameters	Rate of adverse events
Control	Each participant will act as their own control
Research Hypothesis	The investigational headpiece and compatible magnets will provide participants with a retention option that is acceptable for daily use.
Study Schedule	Consent: Participants or will sign an informed consent form prior to the conduct of any study procedures. Baseline: Participants will complete a questionnaire regarding experience with their own headpiece at the time of consenting and enrollment. Follow up: Participants will evaluate the investigational headpiece during a chronic period of up to one-year or until the investigational headpiece receives FDA approval. They will complete questionnaires at two-month intervals. Off-Study: Participants will return their investigational headpieces to the Sponsor.
Experimental Hypothesis	A significant portion of study participants will report that the investigational headpiece is acceptable for wear during daily life.

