Following selection of the headpiece magnet and appropriate fit of the investigational headpiece, the study staff will introduce the Investigational Headpiece questionnaires that participants will complete at the initial visit and two-month intervals throughout their participation in the study. Participants will receive a number of questionnaires that would span the study duration. Pre-paid envelopes will be provided to allow participants to return completed questionnaires every two-months for the duration of the study.

At any time during the study, participants may request meetings with Investigators or Study Staff for changes in magnet strength or adjustments to the investigational headpiece, these meetings will be coordinated through a telephone call, email, or in-person conversation to set up additional visits.

Participants will return the investigational headpiece to the Sponsor at the end of this study. A pre-paid shipping envelope will be provided for this purpose.

Data collection and analysis of the present study will be administered from the Sponsor's location. Recruitment, participant consenting, and fitting of the investigational cochlear implant headpiece may be completed by study staff, with professional training with the Advanced Bionics cochlear implant system, at locations outside of the Sponsor's location. Investigators and study staff will complete training for this study that includes:

- Good Clinical Practice, including investigator responsibilities
- Informed consent procedures, including requirements for inclusion, exclusion, and all foreseeable risks
- Study protocol and procedures
- Processes for recording and reporting adverse events
- Device accountability procedures
- Data collection and correction procedures, source documentation, and record retention requirements

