An unanticipated adverse device effect is any serious adverse effect on: health, safety, or any life threatening problem or death caused by, or associated with a device, if that effect, problem, or death was not previously identified in nature, severity, or degree of incidence in the investigational plan or application, or any other unanticipated serious problem associated with a device that relates to the rights, safety, or welfare of subjects.

All adverse events and adverse device effects, serious and non-serious, will be reported to the Clinical Research Department at Advanced Bionics.

Information to be reported should include, but is not limited to:

- Type/Nature of event
- Date of onset
- Severity
- Duration/rate of resolution
- Course of action taken
- Outcome
- Relationship to investigational materials
- Anticipated or unanticipated
- Other relevant information as necessary

The communication requirements for Adverse Events and Adverse Device Effects are as follows:

Classification	Type of Communication to AB	Communication Time to AB	Contact at AB
Serious Adverse Event	Telephone call and email or FAX notification of adverse event	Within 48 hours of detection	PI
Serious Adverse Device Effect			
Unanticipated Adverse Device Effect	Adverse Event Case Report Form (CRF) with all available information		
Non-Serious Adverse Event	Adverse Event CRF with all available information	Reviewed at monitoring visits	PI
Non-Serious Adverse Device Effect			

Evaluation of any serious adverse events (SAE), serious adverse device effects (SADE), and unanticipated adverse device effects (UADE) will be conducted as follows: Confirmed UADEs will be reported to the IRB within 10 days after receiving notice of the event. Reporting for confirmed SAEs and SADEs will be performed in accordance with local IRB reporting requirements. If it is determined that an event or effect presents an unreasonable risk to

Non-Significant Risk Study of a Cochlear Implant Headpiece

subjects, this study, or those parts of the study presenting that risk, will be terminated as soon as possible. Such termination shall occur not later than 5 working days after the determination is made and not later than 15 working days after the Sponsor first received notice of the effect.

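### The primary safety endpoint counts adverse events, but no procedure schedules asking participants about them, so mild events are likely to be under-counted

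*Protocol*

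**What the plan says.** **Endpoint and commitment.** The synopsis (section 1.0) defines the primary safety endpoint as "Cumulative frequency of adverse events and events per participant". Section 7.0 says "All adverse events will be monitored throughout the duration of the study". Section 7.1 defines an adverse event broadly, whether or not the device is the cause, and adds that "All adverse events and adverse device effects, serious and non-serious, will be reported to the Clinical Research Department at Advanced Bionics".

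**Follow-up.** Section 3.4 describes one fitting visit and then follow-up by post: "Participants will receive a number of questionnaires that would span the study duration", and "Pre-paid envelopes will be provided to allow participants to return completed questionnaires every two-months for the duration of the study". Further meetings take place when the participant asks for a magnet change or an adjustment. The headpiece goes back in a pre-paid shipping envelope.

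**The form.** The Investigational Headpiece Questionnaire in Appendix 2 has two items, acceptability of retention and acceptability of comfort, each on five categories. Its instructions tell a participant with discomfort to stop using the investigational headpiece and go back to their own. They also ask for feedback on the headpiece and magnets when staff request it.

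**Handling of known events.** Section 3.4 lists staff training in "Processes for recording and reporting adverse events". The communication table in section 7.1 has an adverse event CRF, which for non-serious events is "Reviewed at monitoring visits".

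**The concern.** A count endpoint is only as complete as the process that finds the events. Here the protocol fixes the endpoint, the definition and the reporting route, but not the step at which a participant is asked whether anything has happened. Used as printed, the two-monthly form leaves non-serious events to reach the sponsor in two ways: the participant volunteers them, or someone follows up a poor rating without being required to.

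This matters most for the effects that section 4.2 itself anticipates: discomfort, minor skin irritation, and irritation or pain from magnet pressure. People tend not to volunteer complaints of this kind, particularly when setting the device aside resolves them. An event never collected cannot be restored by any later analysis, so this is a matter of study procedure and not one that an analysis plan could repair.

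**Working it through.** The protocol gives no adverse-event rate, detection rate or safety sample-size calculation, so there is no figure to reproduce. The check sets each route by which an event could be recorded against what the protocol says of it.

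1. **Fitting visit (section 3.4).** Staff are present, but the described steps are consent, baseline form, magnet selection and introduction of the questionnaires. Use of the device has only begun.
2. **Two-monthly form (section 3.4, Appendix 2).** This is scheduled, and section 3.6 pays for each form received. It has two items, and neither asks about events. The visible redactions sit in header, ID, date and contact fields; the items are numbered 1 and 2 and followed by the closing line, so a hidden third item is unlikely.
3. **Comfort and retention ratings as indirect signals.** An unfavourable rating does reach the sponsor. No text says that it prompts an adverse-event query or a CRF, and a rating carries no event, onset date or number of events.
4. **Discomfort instruction (Appendix 2).** It says what to do with the device. It does not ask the participant to tell staff.
5. **Meetings on request (section 3.4).** These depend on the participant, and their stated purpose is magnet change or adjustment.
6. **CRF, training, and the 48-hour notice for serious and unanticipated events (sections 3.4, 7.1).** All start from an event already detected. The monitoring visits in the section 7.1 table are where completed CRFs are reviewed. Section 5.6 describes no such visits; its content is that "A data monitoring committee is not needed for this study as there is no significant risk to participants", followed by a reference to the single Principal Investigator.

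None of the six routes is a scheduled question about events.

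**Direction.** Let E be the true number of events, c the share captured (between 0 and 1) and n the number of participants.

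- Recorded events = c × E
- Recorded events per participant = c × E / n

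Both parts of the endpoint are multiplied by c. Since c cannot exceed 1, the bias can only be downward, and it does not shrink as n moves from 20 to 200.

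**Why a low count is ambiguous.** Only the product c × E is observed. The following pairs use rates assumed purely to show this, with one event per affected participant:

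| n | share with an event | share captured | expected recorded |
|---|---|---|---|
| 200 | 5% | 100% | 200 × 0.05 × 1.0 = 10 |
| 200 | 10% | 50% | 200 × 0.10 × 0.5 = 10 |
| 20 | 5% | 100% | 20 × 0.05 × 1.0 = 1 |
| 20 | 10% | 50% | 20 × 0.10 × 0.5 = 1 |

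At each n, a twofold difference in the true rate gives the same expected count. These are not estimates for this trial. The protocol supplies neither rate, so the size of the under-count cannot be computed.

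**The case against.** The strongest reply is that this is silence, not error. Section 7.0 states nothing false, and no section says events will not be asked about. Staff are trained, a CRF exists, and section 5.1 invokes internal SOPs. The SOPs, the CRF and the consent form are not visible, the contact line on the form is redacted, and section 3.4 calls the Appendix 2 forms examples. In addition, the comfort rating is a regular, paid prompt on one of the very risks in section 4.2, and the form foresees staff asking for feedback.

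Part of this stands. The comfort rating is a real signal, and undisclosed material may invite reports. But a signal with no rule attached is not ascertainment, feedback on request has no schedule, and an invitation to report still relies on volunteering. The protocol also prints the follow-up form, so the missing question is visible in what was fixed, not merely left unmentioned.

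Four stronger readings are tempting, and the documents do not support them.

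- *The protocol has no adverse-event procedure.* It has definitions, reporting content, time limits and a CRF. The gap is in detection.
- *Participants are discouraged from reporting.* The form does not ask for a report of discomfort, but nothing in it advises against one.
- *The monitoring visits contradict the postal follow-up.* The table places CRF review there. Nothing suggests that participants attend, so the two need not match.
- *The statement in section 3.4 on collecting no other health-related information rules out event questions.* It belongs to the consent step and need not extend to follow-up.

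It is also fair that the study is a single-group, non-significant-risk study, and that the safety count has no hypothesis, threshold or comparator. Under-counting would therefore overturn no stated decision rule.

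**Conclusion.** The point holds as a cheap improvement. On the page, the primary safety endpoint is a count of all adverse events, no section schedules asking about them, and the one scheduled form contains two acceptability ratings with no link to an event query. That mild events are likely to be under-counted is an inference. It rests on two assumptions: that the procedures are carried out as written, and that minor complaints are volunteered less than completely. The direction is downward for both parts of the endpoint. The size is unknown.

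Because the endpoint is descriptive, the harm is to interpretation: a reader of the final report could not tell whether few events occurred or few were found. A reader might infer that serious events will be missed too, or that the safety result would be invalid. The documents support neither. The argument rests on mild events being volunteered least, and an incomplete count is still informative as a lower bound.

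**What to change.** 1. Add one question to each two-monthly questionnaire: *Since your last form, have you had any new or worsened skin problem, pain or other health problem? Yes / No. If yes: describe it, give the start date, and say whether it is still present.* A Yes triggers the existing adverse event CRF, on which staff complete the remaining details.
2. State in section 3.4 or 7.1 that a comfort rating in either of the two unfavourable categories prompts a staff adverse-event query.
3. Add to the form's instructions a request to tell study staff promptly of any such problem, so that notice does not wait for the next mailing. Leave the stop-use instruction as it is.

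Optional: add one baseline item on skin condition at the headpiece site. Section 7.1 counts worsening of a pre-existing condition as an event, and the baseline form records only two ratings of the personal headpiece. Also reconcile the final follow-up visit, which section 7.1 uses in closing the adverse-event window, with the mail-back close-out in section 3.4. This second item is a wording matter only, since the window is also tied to return to the baseline device.

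**Cost.** Revised forms in three languages, IRB approval, and staff time to follow up positive answers and poor ratings. The reported event rate will probably rise and will include some trivial or unrelated events. Participants who do not return forms will still not be asked, so the number of forms returned should be reported beside the count.

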7.1 Adverse Events and Adverse Device Effects

An adverse event (AE) is defined as any undesirable clinical occurrence experienced by a study subject either during or subsequent to the procedure whether or not it is considered to be device-related.¹ The definition of AE also applies to any event related to any study procedures or to any underlying medical condition, present at baseline, that increases in severity during the study. An underlying medical condition that was present at the time of enrollment will not be reported as an AE, but any increase in severity will be reported as an AE. This definition includes events occurring during the follow-up period and ending when the subject completes the final follow-up visit and returns to use of the baseline device.

A serious adverse event (SAE) is an adverse event that leads to any of the following:

- Death due to any cause
- A life-threatening illness or injury²
- A permanent impairment of a body structure or a body function
- Inpatient hospitalization³, prolongation of hospitalization (extension equal or greater than 24-hours) or surgical intervention to prevent permanent impairment to body structure or body function
- Fetal distress, fetal death, congenital abnormality or birth defect

An adverse device effect (ADE) is any untoward and unintended response to a medical device.

A serious adverse device effect is an adverse device effect that resulted in any of the consequences characteristic of a serious adverse event or that might have led to any of the consequences if suitable action had not been taken or interventions had not been made or if circumstances had been less opportune.

¹ Device-related includes any procedure related to the study device inclusive of placebo.

² Life-threatening refers to an event in which the subject was at risk of death at the time of the event; not an event which hypothetically, if more severe, would be resultant in death.

³ Inpatient hospitalization is defined as a hospital admission for a period of greater than 24 hours.

Non-Significant Risk Study of a Cochlear Implant Headpiece

An unanticipated adverse device effect is any serious adverse effect on: health, safety, or any life threatening problem or death caused by, or associated with a device, if that effect, problem, or death was not previously identified in nature, severity, or degree of incidence in the investigational plan or application, or any other unanticipated serious problem associated with a device that relates to the rights, safety, or welfare of subjects.

All adverse events and adverse device effects, serious and non-serious, will be reported to the Clinical Research Department at Advanced Bionics.

Information to be reported should include, but is not limited to:

- Type/Nature of event
- Date of onset
- Severity
- Duration/rate of resolution
- Course of action taken
- Outcome
- Relationship to investigational materials
- Anticipated or unanticipated
- Other relevant information as necessary

The communication requirements for Adverse Events and Adverse Device Effects are as follows:

Classification	Type of Communication to AB	Communication Time to AB	Contact at AB
Serious Adverse Event	Telephone call and email or FAX notification of adverse event	Within 48 hours of detection	PI
Serious Adverse Device Effect			
Unanticipated Adverse Device Effect	Adverse Event Case Report Form (CRF) with all available information		
Non-Serious Adverse Event	Adverse Event CRF with all available information	Reviewed at monitoring visits	PI
Non-Serious Adverse Device Effect			

Evaluation of any serious adverse events (SAE), serious adverse device effects (SADE), and unanticipated adverse device effects (UADE) will be conducted as follows: Confirmed UADEs will be reported to the IRB within 10 days after receiving notice of the event. Reporting for confirmed SAEs and SADEs will be performed in accordance with local IRB reporting requirements. If it is determined that an event or effect presents an unreasonable risk to

Non-Significant Risk Study of a Cochlear Implant Headpiece

subjects, this study, or those parts of the study presenting that risk, will be terminated as soon as possible. Such termination shall occur not later than 5 working days after the determination is made and not later than 15 working days after the Sponsor first received notice of the effect.

